Participants. We will recruit 5-10 consecutive adult inpatients (dependent on flow within the 6-month treatment window) from the Donnelly units. Inclusion criteria will be:

1. males and females
2. age 18-65 inclusive
3. fluent in English (speaking, reading, and writing)
4. having made a suicide attempt within one week preceding admission. Admission will be defined as admission to either Harford Hospital medical floor (in cases where medical stabilization is required prior to transfer to IOL) or to IOL (in cases where medical stabilization is not required). A suicide attempt will be defined as behavior that is self-directed and deliberately results in injury or the potential for injury to oneself for which there is evidence, whether explicit or implicit, of intent to die.

Exclusion criteria will be:

1. age <18 or ≥66 years old
2. history of schizophrenia spectrum disorder
3. history of mental retardation or organic brain illness
4. current substance use disorder

5. active mania or other psychiatric or medical condition that would preclude informed consent or participation in the trial, in the investigator’s opinion
6. ECT included on patient’s inpatient treatment plan. Patients who are referred for ECT after starting the study will be withdrawn from the study.

Measures. Participants will complete a brief self-report demographic form. Diagnostic status will be measured at pre-treatment using the Diagnostic Interview for Anxiety, Mood, and Obsessive-Compulsive and Related Disorders (DIAMOND).¹⁴ Suicidal ideation and behavior will be assessed using the Columbia-Suicide Severity Rating Scale (C-SSRS).¹⁵ The C-SSRS can be scored to yield an ideation severity score (range 0-5) and a behavior severity score (0-5); suicidal behavior can also be scored dichotomously (present/absent). The C-SSRS will be administered with the timeframe for the “past week” at admission (i.e., pretreatment), and “since admission” at posttreatment, and “past week” at follow-up assessments. Depressive symptoms will be measured using the Structured Interview Guidelines for the Hamilton Rating Scale for Depression (SIGH-D),¹⁶ a well-validated clinician-rated interview for depression. Treatment acceptability will be measured using the Client Satisfaction Questionnaire (CSQ),¹⁷ an 8-item self-report measure.

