Participants will be recruited by a member of the research staff on the day following their inpatient admission or later (for example in the case of a Saturday admission). Patients who meet all of the inclusion criteria and none of the exclusion criteria and agree to participate will provide written informed consent prior to any study procedures. Informed consent will be documented using the Documentation of Informed Consent Form. For patients who are admitted to the hospital involuntarily documentation of competency to provide consent will be completed as well. Only those involuntarily committed patients who have been found competent to provide informed consent for research will be consented. Patients who decline participation will not be approached again. Patients who agree to participation will undergo the informed consent process. This process will involve providing the patient with the informed consent and HIPAA authorization forms to read. The study staff member obtaining consent will highlight the voluntary nature of the research and emphasize that the patient’s decision whether or not to participate will not impact his “usual care” treatment plan; however, patients will also be informed that the information discussed with the study clinician is shared with the inpatient treatment team, and thus may be used by them when making decisions about discharge planning. Patients will be informed that they may keep the forms to review with others if they wish to do so before signing. In addition, all questions the patient has about study participation will be answered prior to obtaining written consent.

Enrolled participants will undergo a clinical assessment by an independent evaluator (IE), who will administer the DIAMOND, C-SSRS, SIGH-D, and IAT.

Participants will receive up to 10 daily sessions of CBT (depending on length of stay), lasting 1.5 hours for the first session and 1 hour for the remaining sessions, following the manualized protocol developed in Phase 1. The CBT protocol is designed to be delivered in two phases. In phase I, the therapist conducts a detailed assessment of the

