4. Effect size (Hedges’s *g*) of IAT D scores from pre- to post-treatment

5. Effect size (Hedges’s *g*) of C-SSRS ideation severity score from pre-treatment through follow-up
6. Effect size (Hedges’s *g*) of C-SSRS behavior severity score from pre-treatment through follow-up
7. Effect size (Hedges’s *g*) of SIGH-D score from pre-treatment through follow-up
8. Effect size (Hedge’s *g*) comparing study enrolled versus study eligible (but not recruited) participants on readmission over the follow-up.

Future Plans. The proposed study will yield feasibility and initial efficacy data that will be used to inform a grant proposal to the American Foundation for Suicide Prevention. That proposal will fund a randomized controlled trial of CBT vs. treatment as usual. Concurrently, we will develop an in-house program to train other staff in the protocol, and will submit a second grant to investigate the efficacy of the training program as well as the efficacy of CBT by those clinicians (benchmarking analysis).

Budget and Budget Justification

[name]. (Principal Investigator, 5% time, no salary requested): [name] will be responsible for overseeing all aspects of the proposed study. He will participate in weekly supervision with the therapist and with consultant [name]. [name] will conduct the outcome analyses and will bear responsibility for publishing the results of the study. [name] will donate his time to the study.

[name]. (Consultant): [name] is a leading expert in CBT for suicide prevention, the author of the treatment protocol used in the proposed study, and was principal investigator on an RCT of that protocol. His involvement is critical for ensuring adequate application of the treatment. [name] will provide a 2-day training for the clinical staff (\$11,000 for his fees plus travel expenses). Following that training, he will participate via videoconference in weekly group supervision meetings during the treatment phase of the study (\$200 x 16 meetings = \$3200).

[name]. (Project Manager, 10% time and salary): [name] will supervise the research assistant and coordinate the day-to-day operations of the study. She will participate in the weekly supervision meetings. She will also listen to audio recordings of at least 10% of all sessions to rate treatment fidelity.

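### Read literally, the post-treatment C-SSRS window opens before the baseline interview and CBT, so pre-CBT ideation or behavior can be carried into the post-treatment score; on either reading its length varies with stay

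*Combined protocol and SAP*

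**What the plan says.** All references are to the combined protocol and SAP.

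- **Measures.** The pre-treatment C-SSRS is "administered with the timeframe for the “past week” at admission (i.e., pretreatment"), and the later windows are "and “since admission” at posttreatment, and “past week” at follow-up assessments". Ideation and behavior severity are each scored 0-5. The section does not say whether a score is the worst level in the window, and it does not explain why the window changes at post-treatment.
- **Participants, inclusion criterion 4.** "Admission will be defined as admission to either Harford Hospital medical floor" when stabilization is needed first, and otherwise as admission to IOL.
- **Procedures.** "Participants will be recruited by a member of the research staff on the day following their inpatient admission or later". Those who agree "will provide written informed consent prior to any study procedures". The independent evaluator then gives the baseline C-SSRS, and up to 10 daily CBT sessions follow, depending on length of stay.
- **Post-treatment assessment (the paragraph after Data Storage and Security).** It follows session 10 or falls in the 24 hours before discharge, whichever is earlier.
- **Analytic Plan.** Outcome 5 is Hedges's g "of C-SSRS ideation severity score from pre-treatment through follow-up". Outcome 6 is the same for behavior severity.

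**The concern.** A pre-to-post contrast needs a post-treatment score that describes the patient after treatment began. If the post-treatment window opens at hospital admission, part of it describes the patient before any CBT, over days the baseline interview has already covered. A patient with severe ideation on the day of admission and none by the last session could correctly receive a high post-treatment rating.

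The window lengths also differ. Baseline and all three follow-up calls look back one week, whereas the post-treatment call looks back over a period set by length of stay.

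The post-treatment interview is the only C-SSRS taken at the end of the inpatient course. There is no concurrent C-SSRS comparison group in which the same distortion would cancel. The pilot efficacy data are a stated aim and are meant to support a later grant proposal, so the inpatient change score should mean what it appears to mean.

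**Working it through.** The plan gives no expected effect or power calculation, so it has no figure to reproduce. The check is window arithmetic.

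**Inputs.** Let admission be day 0, the baseline C-SSRS fall on day d, and k daily sessions follow, with the post-treatment interview on day d + k.
- d is at least 1 (Procedures: recruitment is the day after admission or later, with consent first).
- k is at most 10 (Procedures).
- The baseline and follow-up windows are 7 days (Measures).
- The values d = 3, d = 7, k = 3 and k = 5 are assumptions, used to show a range.

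**Literal reading: the window opens at hospital admission.**
- Post-treatment window = d + k days.
- Days shared with the baseline week = min(d, 7).
- Pre-CBT share of the window = d / (d + k).

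| Baseline day d | k = 10 | k = 5 | k = 3 |
|---|---|---|---|
| 1 | 1/11 = 9% | 1/6 = 17% | 1/4 = 25% |
| 3 | 3/13 = 23% | 3/8 = 38% | 3/6 = 50% |
| 7 | 7/17 = 41% | 7/12 = 58% | 7/10 = 70% |

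The overlap is thus at least about one day for everyone. These are shares of days, not shares of the treatment effect.

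**Alternative reading: admission names the pre-treatment assessment.** The window is k days and the overlap is 0. Its length still runs, for example, from 3 to 10 days, against 7 at the other four time points.

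**Effect on the score, assuming worst-point scoring.** Let A be the worst level between admission and the baseline interview, and B the worst level after it. On the literal reading the recorded score is max(A, B). A window confined to days after the interview gives B. The excess is max(A, B) - B = max(0, A - B), which is never negative. It is zero when ideation before the interview was no worse than after it. It removes the whole drop from baseline when A equals the patient's baseline score.

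**Why the size is open.** The documents do not give the share of patients for whom A equals the baseline level. To show the dependence only, assume:
- baseline scores drawn with mean 4 and SD 1, and post-interview scores drawn independently with mean 2 and SD 1.3, both rounded and limited to 0-5;
- g = mean change / sqrt((var_pre + var_post)/2) × (1 - 3/(4(n - 1) - 1)). With n = 10 the last factor is 1 - 3/35 = 0.914.

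| Share carrying baseline level over | 0% | 10% | 25% | 50% | 100% |
|---|---|---|---|---|---|
| g | 1.58 | 1.34 | 1.06 | 0.68 | -0.09 |

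The result runs from the full effect to none, depending on a quantity the plan does not supply. It is not an estimate for this trial.

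**After the fix.** Overlap is 0 for both scores. The ideation window is min(7, k) days: 7, 5 and 3 for k = 10, 5 and 3. An unrestricted past week would not be enough, because it could still reach back before the interview by up to 7 - k days: 2 days at k = 5 and 4 at k = 3.

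**The case against.** The strongest reply is that admission here names an assessment point, not a calendar event. The same sentence in Measures equates admission with pre-treatment, and the evaluator's entry under Budget and Budget Justification speaks of assessing participants at admission and at discharge. On that reading the behavior window already opens at the baseline interview and nothing is carried over. This is plausible and cannot be excluded, so the overlap holds on the literal reading only. The reply does not remove the stay-dependent window. Nor does it give a uniform direction of bias: under worst-point scoring, a window longer than a week allows more high ratings than baseline did, and a shorter one allows fewer.

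Other replies also have force:
- The medical-floor definition belongs to an eligibility criterion, and nothing says it governs the C-SSRS. A longer overlap after a medical-floor stay is therefore an inference.
- If the baseline past week meant the week before admission, the overlap would vanish. The interview cannot take place before the day after admission, so this is unlikely, and pre-CBT inpatient days would still count at post-treatment.
- Four of the five C-SSRS time points share the past-week window, and SIGH-D also measures pre-to-post change without a since-admission window.
- Any multi-day window with worst-point scoring retains early bad days when a patient is improving. Only part of any masking would come from pre-CBT days.

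A reader might infer that inpatient improvement would be hidden and appear only at the 1-month call, as if it were a post-discharge effect. The documents do not support this: it needs worst-point scoring and near-universal carry-over, and neither is stated. A reader might also infer that the index attempt is counted twice. It precedes admission, so it is not in the post-treatment window. Only behavior between admission and the baseline interview could count at both points in outcome 6.

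**Conclusion.** The concern holds in a limited form. On the literal reading, every participant's post-treatment C-SSRS covers at least about one pre-CBT day that also lies in the baseline week, so earlier ideation or behavior can be, but need not be, carried into that score. On the alternative reading there is no overlap, but the window length still depends on stay and does not match baseline or follow-up.

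If scores are worst-in-window, the literal reading tends to understate pre-to-post improvement in outcome 5. That scoring rule is an assumption, and the size cannot be computed from the documents. The contrasts of baseline with the 1-, 2- and 3-month calls are unaffected. In a single-arm study of 5-10 patients that is not powered for significance, this is a measurement weakness in one time point of two listed outcomes, not a failure of the study. It is worth correcting because the correction costs almost nothing.

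**What to change.** In Measures, replace the post-treatment window as follows:
- **Behavior:** since the pre-treatment interview.
- **Ideation:** the past week, limited to days after the pre-treatment interview.
- **Both:** state how the 0-5 score is formed (for example, whether it is the worst level in the window) and record the window length for each participant.

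A 48-hour ideation rating at both pre- and post-treatment could be added to give a pair of equal windows. It is optional, since it means extra items at two visits.

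The main change is a sentence in Measures and matching wording on the rating form, with no extra visit. It has three limits. In short stays the ideation window is under 7 days, so its length must be reported with outcome 5. The behavior window still lengthens with stay, which is why its length should be recorded too. If a baseline interview falls more than 7 days after admission, the earliest inpatient days are in neither window; recording the days from admission to the interview will show whether this happens.

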Participants will then meet with the IE again for the C-SSRS, SIGH-D, IAT, and CSQ after the 10th session or within 24 hrs. prior to discharge, whichever comes first. After discharge, participants will have a telephone interview at 1 month, 2 month, and 3 month follow-up. The IE will administer the C-SSRS during these calls. Chart review (via Epic) will also be completed on study eligible participants (whether or not recruited). Data retrieved at 1, 2, and 3-month post-discharge will include readmission rates to the IOL or ED. Whether suicide attempt preceded admission will also be recorded. Demographic and clinical information will also be collected from the medical record (age when < or = 89, sex, race/ethnicity, diagnoses, medication, length of stay, suicide method) to compare study eligible participants who were versus were not recruited to determine if the groups were matched on these variables. At least three telephone calls will be made to try to reach a participant to complete the follow-up assessments. If a participant is unable to be reached by phone for the follow-up assessment after three tries then a letter will be sent to the participant asking them to contact the IE to inform her whether or not they wish to continue in the study. If a participant fails to contact the IE within 1 week of the study team sending the letter then a second letter will be sent again requesting that the participant contact the IE to let her know whether or not they wish to continue in the study along with a date by which the participant should contact the IE. If the participant does not contact the IE by the date stated in the letter they will be withdrawn from the study.

Adverse Event reporting.

Any severe adverse events (SAEs) that occur will be reported to the HHC IRB in a timely fashion, according to policy 901. Unexpected Severe AE’s – those rated 3-5 – will be reported within 7 calendar days of learning of the event.

Analytic Plan. It is noted that this is an initial test of feasibility and is therefore not powered for statistical significance. Though we will conduct significance tests, of greater importance are the following outcomes (all analyses will be intent-to-treat):

1. Mean CSQ scores at post-treatment, indicating acceptability of treatment.
2. Percent attrition rate, indicating acceptability of treatment.
3. Mean treatment fidelity rating, indicating our capacity to administer the treatment as described.

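### Length of stay is settled after enrolment and may be touched by the study in one group only, so it should not count as evidence that enrolled and not-recruited patients were matched

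*Combined protocol and SAP*

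**What the plan says.** The chart-review paragraph, which follows the post-treatment assessment and telephone follow-up text, covers all eligible patients, recruited or not. It collects age, sex and race/ethnicity, and then "diagnoses, medication, length of stay, suicide method) to compare study eligible participants who were versus were not recruited". The purpose is "to determine if the groups were matched on these variables". No time point is given for medication. No rule says what follows if the groups differ.

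Three statements in the Procedures text bear on when length of stay is determined:

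- Enrolment: patients are "recruited by a member of the research staff on the day following their inpatient admission or later".
- Discharge: patients are told that what is said to the study clinician "is shared with the inpatient treatment team, and thus may be used by them when making decisions about discharge planning".
- Treatment: participants receive "up to 10 daily sessions of CBT (depending on length of stay").

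Item 8 of the Analytic Plan then compares the same two groups on readmission, as a Hedges's g. Readmissions are retrieved at 1, 2 and 3 months after discharge.

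**The concern.** A matching check supports a non-randomised comparison only if its variables were settled before the groups separated. Age, sex, race/ethnicity and suicide method meet that condition, and admission diagnoses would too. Total length of stay does not, because it is known only at discharge, after enrolment and after the CBT sessions.

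Two things can then move it. One is selection: a patient who goes home before being approached cannot be enrolled but can be a comparator. The other is a possible effect of the study, through the information passed to the inpatient team for enrolled patients only. A gap in stay could be taken as a sign of different patients when part of it came from participation. Equal stays could be taken as a sign of similar patients when two effects had offset each other.

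What is at stake is how outcome 8 is interpreted. It is the only one of the eight listed outcomes that compares groups, it is in the list that the Analytic Plan ranks above the significance tests, and the matching check is the only protection stated for it.

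**Working it through.** The plan gives no figure on this point, so there is none to reproduce. The check is one of timing, followed by an illustration on assumed values.

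**1. Order of events**

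| Step | Source | Enrolled | Not recruited |
|---|---|---|---|
| Admission | Participants | yes | yes |
| Still in hospital the next day or later | Procedures, recruitment | required | not required |
| Study-clinician information may reach discharge planning | Procedures, consent | yes | no |
| Discharge, when total stay is fixed | follows from the above | yes | yes |
| Readmission counted from discharge | chart review; Analytic Plan item 8 | yes | yes |

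The second row rests on a plain reading of eligibility. None of the inclusion or exclusion criteria asks whether the patient was still in hospital when staff could first approach, so an early leaver counts as eligible and not recruited.

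**2. What a gap in stay contains**

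Observed gap (enrolled minus not recruited) = S + B + E, where

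- S = selection, because early leavers can only be comparators;
- B = other differences between patients who were and were not recruited;
- E = any effect of participation on stay.

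The check is meant to show B. It yields one number for three unknowns, and the documents give no value for any of them.

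**3. Illustration of S (all values assumed)**

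Take stays as gamma-distributed with mean 7 and SD 5 days. Nobody who leaves before day k is recruited, and a random half of the rest are. B and E are zero. Simulated means:

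| k (days) | Enrolled | Not recruited | Gap | Gap / 5 |
|---|---|---|---|---|
| 1 | 7.23 | 6.78 | 0.45 | 0.09 |
| 2 | 7.75 | 6.40 | 1.35 | 0.27 |
| 3 | 8.41 | 6.08 | 2.33 | 0.47 |

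In this set-up, dropping early leavers from the comparator brings the expected gap to zero, because both groups are then random halves of the same patients.

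**4. Illustration of E (all values assumed)**

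Standardised gap = shift / SD, with S and B zero.

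- SD 4 days, shift of 1 to 3 days: 1/4 = 0.25 to 3/4 = 0.75.
- SD 6 days, shift of 1 to 3 days: 1/6 = 0.17 to 3/6 = 0.50.

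If the check were a two-sided 5% test (the plan does not say), the chance of flagging the gap is about Φ(d/√(1/n₁ + 1/n₂) − 1.96), with d the standardised gap. With 10 enrolled:

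- lowest: d = 0.17, 10 comparators, 0.056;
- highest: d = 0.75, 30 comparators, 0.537.

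So about 6% to 54%, and lower with five enrolled.

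**5. The two together**

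At k = 2, S is +1.35 days. If E were −1.35, the gap would be 0 and the groups would look alike. If E were +1, the gap would be 2.35. Neither result says anything about B. The direction of E is unknown.

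**The case against.** The strongest reply is that nothing in the analysis depends on the check. The chart-review paragraph sets no threshold, adjustment or exclusion, and item 8 is an unadjusted effect size. Length of stay cannot change the estimate. This stands, and it limits the point to how the result is read.

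A second reply is that the gap from early leavers is a real difference arising before enrolment, which a comparison of stay would help to reveal. This stands in part: that component is selection, not a study effect. It is better removed by defining the comparator than inferred from a variable that may also carry a study effect.

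A third reply is the consent assurance that the patient's "decision whether or not to participate will not impact his “usual care” treatment plan". It does not settle the matter, because the same sentence goes on, with a contrasting conjunction, to describe the sharing with the inpatient team.

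A reader might infer more than the documents support:

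- *That CBT lengthens stay so that sessions can be completed.* The plan has it the other way round. Stay limits the number of sessions, and the post-treatment assessment is brought forward if discharge comes before session 10.
- *That session content is routinely built into discharge decisions.* The text says it may be used.
- *That the medication comparison is faulty.* It would be if medication were recorded after enrolment, but no time point is given, so this needs clarifying only.
- *That readmission itself is shown to be biased.* Both groups are counted from discharge, and nothing in the documents links stay to readmission risk.

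**Conclusion.** The point holds, as a cheap improvement. Total length of stay is determined after enrolment, and the plan's own consent wording allows the study to influence it in enrolled patients only. It therefore cannot show whether the groups were matched: a difference, or no difference, mixes selection with a possible study effect.

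The size of either component cannot be derived from the documents. The illustrations show only that gaps of roughly 0.1 to 0.75 SD could arise without any other baseline difference, under assumed stays, shifts and group sizes. The conclusion rests on two readings: that early leavers count as eligible but not recruited, and that length of stay means the whole admission. The consequence is modest, since the study enrols 5-10 patients, is declared unpowered and plans no step that uses the check. It is worth correcting because outcome 8 has no other stated safeguard and the results are meant to inform a grant proposal for a randomised trial.

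**What to change.** Reword the chart-review paragraph and item 8 of the Analytic Plan:

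1. Base the matching check on values fixed at admission: age, sex, race/ethnicity, admission diagnoses, medication at admission and suicide method.
2. Report total length of stay separately for each group as a post-entry descriptor, not as evidence of matching.
3. For outcome 8, restrict comparators to eligible patients still in hospital on the first day they could have been recruited: the day after admission, or the next recruiting day. Say which admission starts the count, since the Participants section allows either the medical floor or the psychiatric unit.
4. Show the unrestricted comparison as a sensitivity result.

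The cost is a change of wording and the use of admission and discharge dates that length of stay already requires. No patient contact or care changes. The downside is that a few early-discharge comparators leave the main comparison. Under the assumed distribution in the working, the share lost is p / (p + (1 − p)/2), with p the proportion who leave before day k. For k = 1, p = 0.036, so 0.036/0.518 = 7% of comparators. If every patient had to wait until day 2, p = 0.116, so 0.116/0.558 = 21%. The sensitivity result keeps those patients in view.

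### Withdrawing a participant after one unreached follow-up assessment and two unanswered letters can forfeit later C-SSRS calls; still attempting the budgeted calls is a cheap improvement, not a correction of an error

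*Combined protocol and SAP*

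**What the plan says.** The follow-up paragraph, printed just before Adverse Event reporting, sets three calls after discharge at which the independent evaluator (IE) gives the C-SSRS. The trigger for letters is a single missed assessment: "If a participant is unable to be reached by phone for the follow-up assessment after three tries then a letter will be sent". After a further week without contact a second letter goes out, "along with a date by which the participant should contact the IE"; the length of that period is not given. The sequence ends: "If the participant does not contact the IE by the date stated in the letter they will be withdrawn from the study".

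Participants, exclusion criterion 6, has a second route out: "Patients who are referred for ECT after starting the study will be withdrawn from the study". Neither place separates leaving treatment from leaving assessment, or says whether later calls are still made.

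The Analytic Plan states that "all analyses will be intent-to-treat". Outcomes 5 and 6 are effect sizes for C-SSRS ideation and behavior severity running through follow-up. Outcome 2 is percent attrition, read as acceptability of treatment, with attrition not defined. Separately from the calls, "Chart review (via Epic) will also be completed on study eligible participants (whether or not recruited"), covering readmission at 1, 2 and 3 months, and "Whether suicide attempt preceded admission will also be recorded". The budget pays for three follow-up interviews for each of 10 participants.

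**The concern.** Someone missed in month 1 may be reachable in month 2 or 3, yet the rule treats silence as departure. The telephone C-SSRS is the only follow-up source for outcomes 5 and 6. It asks about the past week (Measures), so a later interview cannot recover a skipped one. With 5 to 10 participants, one or two interviews lost by rule are visible. The three calls also cover the 90 days after hospitalization that the Rationale singles out as high risk.

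Two lesser matters follow from the same withdrawal wording. An ECT referral before the post-treatment visit can cost that visit as well as the calls. And if every withdrawal counts as attrition, ECT referral and lost phone contact would be read automatically as low acceptability of CBT, in data meant to support a grant proposal.

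**Working it through.** **Plan's own figure.** Participant Remuneration: $50 × 3 × 10 = $1500, which reproduces. It covers 30 interviews at n=10; at n=5 the planned number is 15.

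**Loss per person (no contact rate needed).**
- Month-1 miss: up to 2 later interviews, 2/30 = 6.7% or 2/15 = 13.3%.
- Month-2 miss: up to 1, so 1/30 or 1/15.
- Month-3 miss: none.
- ECT withdrawal before post-treatment: up to 4 C-SSRS interviews (post-treatment plus three calls) and the CSQ, IAT and SIGH-D, since "Participants will then meet with the IE again for the C-SSRS, SIGH-D, IAT, and CSQ after the 10th session" or just before discharge.

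**Expected loss (assumptions needed).** The documents give no contact or letter-reply rate. Assume:
- each person has a monthly contact probability p, with mean q = 0.8 across people and within-person correlation rho (beta-binomial);
- a missed person answers a letter and stays in with probability r;
- s = p + (1−p)r is then the chance of remaining in after one call.

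Without the rule, 10 × 3 × 0.8 = 24.0 interviews are expected. The open date in the second letter allows two timings.

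- *Withdrawal before the next call:* lost = 10 × [(q − E[ps]) + (q − E[ps²])].
- *Withdrawal after the next call:* a month-1 miss costs only month 3 and a month-2 miss costs nothing, so lost = 10 × (q − E[ps]).

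With independent contacts (rho = 0):
- r = 0: s = 0.8. Before: 10 × [(0.8 − 0.64) + (0.8 − 0.512)] = 4.48. After: 10 × 0.16 = 1.6.
- r = 0.5: s = 0.9. Before: 10 × [(0.8 − 0.72) + (0.8 − 0.648)] = 2.32. After: 10 × 0.08 = 0.8.
- r = p: s = 0.96. Before: 10 × [(0.8 − 0.768) + (0.8 − 0.737)] = 0.95. After: 10 × 0.032 = 0.32.

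For r = 0 and r = 0.5 these are the maxima over rho. For r = p the maxima, from exact beta moments, are 1.08 (rho about 0.18) and 0.385 (rho about 0.22). At rho = 1 each person is always or never reached, and every loss is 0.

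| Letter reply | Lost if withdrawal precedes next call | Lost if it follows next call |
|---|---|---|
| Follows the person's reachability (r = p) | 0 to 1.1 | 0 to 0.4 |
| Half reply | 0 to 2.3 | 0 to 0.8 |
| None reply | 0 to 4.5 | 0 to 1.6 |

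**Sensitivity to q**, no replies, rho = 0:
- q = 0.7: 10 × [(0.7 − 0.49) + (0.7 − 0.343)] = 5.67 before, 2.1 after.
- q = 0.9: 10 × [(0.9 − 0.81) + (0.9 − 0.729)] = 2.61 before, 0.9 after.

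**Extra contact rounds if later calls are kept**, q = 0.8, withdrawal before the next call: 10 × [(1 − E[s]) + (1 − E[s²])].
- r = p: 1.18 to 4.00.
- r = 0.5: 2.50 to 2.90.
- r = 0: 4.00 to 5.60; at rho = 0 this is 10 × (0.2 + 0.36) = 5.6.

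That is about 1 to 6 rounds. If withdrawal follows the next call it is 10 × (1 − E[s]), at most 10 × 0.2 = 2.0.

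**Attrition.** If all withdrawals count, each adds 1/10 = 10 points (n=10) or 1/5 = 20 points (n=5).

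**The case against.** The rule has a purpose. Both letters ask whether the person wishes to continue, so this is partly a check on consent to contact. Participants have recently attempted suicide, some may be involuntary admissions, and the consent procedure stresses voluntariness. Stopping after three calls and two letters is defensible, and an ethics board might prefer it. That trade-off stands; a stated opt-out narrows it but does not remove it.

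The end of assessments is inferred. The documents do not state it, and the consent pages, which might cover contact after withdrawal, are not in the copy reviewed. This stands too, and is why the point is worded as what the rule can forfeit.

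The size is uncertain. The largest losses combine contacts that are independent from month to month with nobody ever answering a letter, an unlikely pairing. They also need withdrawal to take effect before the next call. If being reached at that next call cancelled the withdrawal, the loss would be smaller still.

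On ECT, planned ECT is already an exclusion, and in a single-arm pre-post study scores after ECT say little about CBT. That is largely right and makes this part secondary. On attrition, silent disengagement may itself signal low acceptability, so loss of contact cannot simply be set aside as unrelated to CBT.

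**Conclusion.** The point holds as a cheap improvement. The non-contact rule can cost up to two later C-SSRS interviews per participant missed at month 1. This affects outcomes 5 and 6 only: the calls carry no other scheduled instrument, and chart review still supplies readmission for outcome 8 and whether an attempt preceded it. At an assumed contact probability of 0.8, the most that would be lost among 10 participants is 1.1, 2.3 or 4.5 interviews (by reply assumption) if withdrawal precedes the next call, and about 0.4, 0.8 or 1.6 if it follows. All approach zero if the same people stay unreachable. These figures rest on assumed contact and reply rates and on the reading that withdrawal ends the calls.

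Three stronger readings are not supported:
- A reader might infer that the rule contradicts intent-to-treat. It does not; a withdrawn participant can stay in the analysis set without later scores.
- A reader might infer that post-discharge attempts go unobserved. Chart review records attempts that led to a captured admission, though it gives no C-SSRS scores.
- A reader might infer that the attrition figure will understate acceptability. Outcome 2 is undefined, so it is not known which withdrawals count, and some silence may reflect low acceptability.

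**What to change.** **Main change.** Record non-response as a missed assessment and still attempt the later scheduled calls unless the participant withdraws consent. State a simple opt-out in the consent form and in both letters. If the sponsor already intends to keep calling, one clarifying sentence is enough.

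**Secondary.**
- For participants withdrawn on ECT referral, keep the already scheduled assessments where they consent, flag them, and show results with and without them. The clinical handling of ECT and CBT is left unchanged.
- Report attrition by reason and phase: participant stopped CBT, ECT referral, not reached after discharge. Do not automatically read the last two as low acceptability of CBT, and note that silent disengagement may partly reflect it.

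**Cost.** A short protocol edit, possibly with consent-form and IRB wording. At contact 0.8, about 1 to 6 extra contact rounds in total for 10 participants, by the existing evaluator. An unsuccessful round means at least three calls, plus letters if those are repeated. No interview payments are needed beyond the budgeted $1500. The real downside is renewed calls to people who have not answered, which the present rule avoids.
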